9.3 Safety monitoring

The incidence of adverse events will be recorded throughout the duration of the study and at the safety follow up visits. The trial will be stopped if there is a significant ($P = 0.01$) incidence of severe adverse events or any event arises which renders continuation of the study not to be in the interests of participants.

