Clinical trials of NIR laser treatment for centre involving diabetic macular oedema (see clinicaltrials.gov #NCT00846092 for a study in Wisconsin) have started but no well-conducted study has reported its' results yet

The NIRD Trial described here improves on the Wisconsin Study and the Stokes Study (in which the patients administered the treatment themselves at home using an NIR light emitting diode (LED) [10] through the use of a slit lamp biomicroscope mounted NIR laser generated light source to be administered to the patient in a consulting clinic. This ensures that the amount of treatment is delivered at an accurate predetermined dose only to the part of the retina where it is required.

Review of safety post enrolment of the first cohort in the NIRD study has shown the NIR light to be safe. Results also indicate that a delayed beneficial effect may be present post completion of NIR treatment.

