2.2.2 Secondary Outcome measures at 1month, 8 weeks, 12 weeks and 16 weeks

- Best corrected LogMAR Visual Acuity (VA)
- Time to oedema reduction
- Time to oedema recurrence
- FFA assessment of leak and area of ischemia before and after intervention
- Change in retinal sensitivity (dB) as measured by microperimetry from Baseline to Week 5, 8, Week 16 and 6 month visit.

2.2.3 Safety outcomes will be:

- Any loss of VA
- Any increase in macular thickness as measured by OCT

3 Design

A cohort of 21 patients satisfying the inclusion criteria will be recruited from the outpatient hospital clinic. They will be sequentially allocated into one of three groups. Each group will have seven patients with group 1 enrolment completed first, followed by group 2 and finally, group 3. Each group will be managed identically but will receive a different dose of NIR energy.

Group 1 will be treated with a dose of 25 mW/cm² for 90 seconds (now fully enrolled)

Group 2 will be treated with a dose of 100 mW/cm² for 90 seconds (now fully enrolled)

Group 3 will be treated with a dose of 200 mW/cm² for 90 seconds.

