3.2 Organisational Structure of the Study Group

The centre will have trained BCVA examiners, a study coordinator, a photographer, an ophthalmologist performing the NIR laser light delivery, and an optical coherence tomography (OCT) examiner. There will be no masking in this study.

4 Participant Eligibility

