7.3 Treatment of Adverse events

7.3.1 Introduction

Adverse Event Definition: Any undesirable clinical occurrence in a subject whether it is considered to be device related or not, that includes a clinical sign, symptom or condition and/or an observation of an unintended technical performance or performance outcome of the device.

Examples of an AE **include**:

- Exacerbation of a chronic or intermittent pre-existing condition including either an increase in frequency and/or intensity of the condition.
- New conditions detected or diagnosed after investigational treatment administration.
- Signs, symptoms, or the clinical sequelae of a suspected interaction.
- Signs, symptoms, or the clinical sequelae of a suspected overdose of a concurrent medication (overdose per se should not be reported as an AE/SAE).

This trial is being carried out in the facilities of quaternary ophthalmic referral centre with extensive experience in laser therapy. The medical staff are well experienced in dealing with all adverse events associated with laser therapy.

Adverse events will be collected from the first NIR laser treatment visit, not necessarily from the date of consent in the event that the patient is not treated on the same day as they are consented. The incidence of adverse events will otherwise be recorded throughout the duration of the study and at the safety follow up visit. These will be graded by the Principal Investigator as mild, moderate or severe.

Serious Adverse Event Definition: Any untoward medical occurrence that:

- results in death;
- is life-threatening;
- requires inpatient hospitalization or prolongation of existing hospitalization;
- results in persistent or significant disability/incapacity; or
- is a congenital anomaly/birth defect

For SAE's the relationship to study treatment will be graded as related, unrelated, probable, unlikely or likely. SAE's will also be graded as expected or unexpected

Serious adverse events (SAE's) as defined by the International Conference on Harmonisation, Good Clinical Practice (ICH-GCP) as per above will be reported as SAE's to the approving HREC according to local requirements.

The following events are to be considered adverse events but not serious adverse events and therefore reporting as SAE's is not required:

- Hospitalizations for elective surgery
- Hospitalizations for admissions of less than 24 hours in duration

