7.3.3 Recording AEs and SAEs

When an AE/SAE occurs, it is the responsibility of the investigator to review all documentation (e.g. hospital progress notes, laboratory, and diagnostic reports) relative to the event. The investigator/site staff will then record all relevant information regarding an AE/SAE in to the eCRF. Any SAE documentation forwarded to TGA/HREC will be de-identified maintaining patient anonymity. For each adverse event, start and stop dates, action taken, outcome, intensity (see Section 7.3.1) and relationship to study treatment and causality must be documented.

The investigator will attempt to establish a diagnosis of the event based on signs, symptoms, and/or other clinical information. In the absence of a diagnosis, the individual signs/symptoms should be documented.

8 Endpoints

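### The P = 0.01 stopping limb in Protocol 9.3 cannot be applied as written, because no reference rate, comparator or denominator is stated

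*Protocol*

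**What the plan says.** Protocol 9.3 has two stopping limbs joined by an or. The statistical limb reads: "The trial will be stopped if there is a significant ($P = 0.01$) incidence of severe adverse events". The judgement limb applies if "any event arises which renders continuation of the study not to be in the interests of participants". Section 9.3 names no test, reference rate, comparison or denominator, and points to no other document for them.

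The design offers no obvious comparator. All three groups receive NIR and differ only in dose (25, 100 or 200 mW/cm²). Section 3 adds: "Each group will have seven patients with group 1 enrolment completed first, followed by group 2 and finally, group 3". Groups 1 and 2 are described there as fully enrolled. Section 3.2 states: "There will be no masking in this study". Section 1.4 applies no power calculation, so no event rate is assumed there either. The background (2.1) reports only a qualitative safety result: "Review of safety post enrolment of the first cohort in the NIRD study has shown the NIR light to be safe".

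On the events themselves, 7.3.1 defines an adverse event as "Any undesirable clinical occurrence in a subject whether it is considered to be device related or not", collected from the first laser visit to the 6-month safety visit. On intensity it says: "These will be graded by the Principal Investigator as mild, moderate or severe". Section 7.3.3 requires for each event that "intensity (see Section 7.3.1) and relationship to study treatment and causality must be documented".

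**The concern.** A P-value needs a null hypothesis, and this rule has none. There is no untreated or sham arm to supply one, and no expected rate is written down. Zero is not a safe default: the adverse event definition takes in events unrelated to the device, over about six months, in people with diabetes, so some background of severe events is plausible.

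Enrolment now concerns group 3, at the highest dose. If severe events appear there, two people applying 9.3 in good faith could reach opposite decisions from the same data, depending on a reference rate and denominator that each has to supply. A mandatory safety rule should not leave that open.

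**Working it through.** **Plan's own figure.** The plan gives a threshold, P = 0.01, but no event count to reproduce. The check is therefore whether the threshold fixes a count.

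**Inputs.** From the protocol: level 0.01 (9.3); 7 patients per group and 21 in total, all treated (1.3, 3). Assumed: severe means the 7.3.1 intensity grade; the unit is the patient; the test is a one-sided exact binomial; the reference rate p0 lies between 0.1% and 30%. The protocol supplies none of these four.

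**Step 1: count implied by the threshold.** Find the smallest c with P(X ≥ c | n, p0) ≤ 0.01, where X is binomial.

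| Assumed p0 | c of 7 | P | c of 21 | P |
|---|---|---|---|---|
| 0.1% | 1 | 0.0070 | 2 | 0.0002 |
| 1% | 2 | 0.0020 | 3 | 0.0012 |
| 2% | 2 | 0.0079 | 3 | 0.0081 |
| 5% | 3 | 0.0038 | 5 | 0.0032 |
| 10% | 4 | 0.0027 | 7 | 0.0033 |
| 20% | 5 | 0.0047 | 10 | 0.0041 |
| 30% | 6 | 0.0038 | 12 | 0.0087 |

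The same words can mean 1 to 6 patients in one group. The n = 21 columns show only how much the unstated denominator matters; they are not a proposed rule.

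**Step 2: same data, different decision.** Suppose 2 severe cases in group 3 and none in groups 1 and 2.

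- 2 of 7 against 1%: P = 1 − 0.99⁷ − 7(0.01)(0.99⁶) = 0.0020, stop.
- 2 of 7 against 2%: P = 0.0079, stop.
- 2 of 7 against 5%: P = 1 − 0.95⁷ − 7(0.05)(0.95⁶) = 1 − 0.6983 − 0.2573 = 0.044, continue.
- 2 of 21 against 1%: P = 0.019, continue.
- Group 3 against the other 14 (Fisher's exact test, 2/7 v 0/14): P = 0.10, continue.

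The protocol proposes none of these comparisons. A comparison between doses would also miss harm common to all doses.

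**Step 3: what a 0.01 rule can detect in seven patients.** If the true group 3 rate were 30%, the Step 1 count is reached with probability 67% for c = 2 (p0 of 1% or 2%), 35% for c = 3 (5%), 13% for c = 4 (10%) and 3% for c = 5 (20%).

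**Step 4: a fixed count of 2 of 7.** P(X ≥ 2) = 1 − (1 − p)⁷ − 7p(1 − p)⁶, where p is the rate of whichever event the rule counts.

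- True rates of 20%, 30%, 50%: 42%, 67%, 94%.
- Assumed background rates of 1%, 2%, 5% for that same event: 0.2%, 0.8%, 4.4%.

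Stopping as soon as the count is reached does not change these probabilities, because the number of affected patients can only rise.

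**The case against.** The strongest reply is that little depends on this limb. The limbs are alternatives, and the judgement limb is the wider one: a single event suffices, without a P-value. The unusable limb can only add stops; it cannot prevent one. Step 3 shows that a 0.01 rule in seven patients adds little unless the reference rate is low. Other protections bear directly on ocular harm: discontinuation of study treatment at a 100-micron increase or a 10-letter loss (6.4); visual acuity, OCT and fundus examination before laser each Friday of weeks 1 to 4 (6.5, 15); shielding of the central 1 mm (1.3, 6, 10.1); doses enrolled in ascending order (3); and reporting of serious events to the ethics committee (11.2). All of this stands. A reader might infer that the trial has no working safety stop, and the documents do not support that.

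A second reply is that a statistical analysis plan or monitoring document may define the test. It may, so a reader should not infer that no count exists anywhere for this trial. But 9.3 did not leave the rule to a later document. It fixed a numerical criterion in the protocol, and that criterion has no meaning on its own terms.

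Third, every reference rate above is assumed, and the two-case example is hypothetical. That is correct. They demonstrate ambiguity and do not estimate harm. The need to assume a rate is itself the defect.

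**Conclusion.** The point holds for the statistical limb of 9.3 only. As written, that limb does not determine how many affected patients stop the trial: over assumed reference rates of 0.1% to 30% the answer runs from 1 to 6 of 7. This rests on reading severe as the 7.3.1 grade and on a one-sided exact binomial test; other readings would add to the spread.

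The practical consequence is limited, because the judgement limb and the patient-level safeguards remain in force. What is lost is an objective trial-level trigger in an unmasked study as it reaches its highest dose. The rule should be corrected, but it does not show that participants are unprotected.

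**What to change.** In 9.3, replace the P-value wording with an explicit number of group 3 patients (n = 7, 200 mW/cm²) with a severe adverse event by the 7.3.1 grade, applied as soon as it is reached. State whether all severe events count or only treatment-related ones. Keep the judgement limb unchanged. Two forms are acceptable:

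- **A low fixed count without a P-value**, such as 2 of 7. Its performance is given in Step 4, provided the rates are read as those of the event actually counted. If only treatment-related events count, the relevant background rate is the rate for those events.
- **A count from a one-sided exact binomial test at 0.01** against a stated reference rate approved by the ethics committee, for example 3 of 7 at an assumed 5% (P = 0.0038). Step 3 shows the price in power.

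A cumulative count over all 21 patients is not advisable now. Groups 1 and 2 are fully enrolled and some of their events may already be known, so such a count would not clearly be fixed in advance.

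The cost is one sentence, submitted as an amendment for ethics approval under 11.3, and agreement on a count or a reference rate. No new data are needed, since intensity and relationship to treatment are already recorded under 7.3.3.

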9.4 Electronic Case Report Form (eCRF)

An electronic case report form will be completed for each patient for each study visit summarising all of the screening and study data. Patients will be referred to by their study identification code only to retain confidentiality within the database.

10 Investigational Equipment

10.1 Description

The Ellex Integre NIR Laser is a slit lamp microscope mounted 670nm light source that can be varied in brightness by the operator to set the required power density from 50 to 500 mw per square centimetre. This level is between 1x and 10x the brightness of the NIR LED device used in the Wisconsin Study but even at the highest level of intensity is only just comparable to the energy density of the aiming laser used in a standard thermal laser photocoagulator. At its highest brightness this is 50X lower in energy density than a photocoagulator. As an additional safety measure the Ellex Integre NIR laser beam is 4.5mm in diameter with a central masked area of 1.0 mm diameter in order to avoid illuminating the central macula with light.

The Ellex Integre NIR Laser system has a user selectable exposure duration control permitting the user to preset the treatment time duration.

10.2 Maintenance of Machine/Equipment

The Ellex Integre NIR laser equipment will be installed and calibrated at the start of the trial and inspected and tested for accurate calibration at least annually for the duration of the trial.

11 Administration Procedures

11.1 Ethical Considerations

Information on the ELLEX Integre laser is summarised in Section 10

This study will be carried out according to the Declaration of Helsinki, the NHMRC National Statement on Ethical Conduct in Research Involving Humans (2007) and the Notes for Guidance on Good Clinical Practice as adopted by the Australian Therapeutic Goods Administration (2000) (CPMP/ICH/135/95) and the ICH GCP Guidelines.

11.2 Human Research Ethics Committee

The Protocol will be submitted for approval to the site's Human Research Ethics Committee (HREC), and written approval obtained, before volunteers are recruited and patients are enrolled. It is the responsibility of the Investigator to report study progress to the HREC as required or at intervals not greater than one year.

The Principal Investigator, or his/her nominee, will be responsible for reporting any serious adverse events to the HREC as soon as possible, and in accordance with the local guidelines of the HREC.

11.3 Protocol Amendments

Protocol modifications that impact on patient safety or the validity of the study will be approved by the HREC. If a Protocol amendment requires changes to the Informed Consent Form, the revised Informed Consent Form, prepared by the Investigator, must be approved by the HREC.

The original signed copy of amendments will be kept in the Study File with the original Protocol. It should be noted that where an amendment to the Protocol substantially alters the study design or the potential risks to the patients, each Patient's consent to continue participation should be obtained.

11.4 Protocol Compliance

The instructions and procedures specified in this Protocol require diligent attention to their execution. If any patient is treated in a manner that deviates from the Protocol, the nature and reasons for the Protocol violation shall be recorded as a note to file and kept in the site study files. The Investigator and designees will comply with all applicable federal, state and local laws.

12 Photography / Fluorescein Angiography

12.1 Fundus Photography

Fundus camera photography for FFAs and colour photographs are to be performed digitally. All digital images will be de-identified for grading.

12.2 Fundus Colour Photographs

Non stereo 3-Field, ETDRS digital images should be captured at an angle of 30 degrees. If the 30 degrees angle is not an option then 35 degrees can be used. Images will be taken at baseline, week 5, week 16 and 6 month follow up visit or early exit visit.

12.3 Fluorescein Angiography

Fluorescein injection: 5ml of 10% sodium fluorescein will be rapidly injected into the antecubital vein. Other injection sites may be substituted if necessary.

Standard angiogram will be presented as 4 UP (RF, <30sec, 60-90 sec, 5 min) at baseline, Week 5 and week 16 or early exit visits.

13 Optical Coherence Tomography & Fundus Autofluorescence

13.1 OCT Examination Procedure

The eyes should be maximally dilated to help ensure optimal quality scans.

[figure not shown]
Spectralis OCT: The volume scan is used to calculate the different thickness map parameters for statistical analysis of the outcome data. Cross hair Scan of both horizontal and vertical line is used to demonstrate cystic macular oedema

Cirrus OCT: The Macula Thickness: Macula Cube 512 x 128 scan is used to calculate the different thickness map parameters for statistical analysis of the outcome data. The HD 5 Line Raster is used to demonstrate cystoid macula oedema.

13.1 Fundus Autofluorescence Procedure

Must be performed prior to fluorescein angiography. Non stereo, Fundus Autofluorescence images should be captured at an angle of 35 degrees with the Heidelberg Spectralis or Zeiss Topcon using the Autofluorescence setting. The images should be captured using the ART mode. Autofluorescence is performed at the baseline, Week 5 and week 16 or early exit visits.

14 Ellex Integre NIR Laser

15 Schedule of Visits

	Screen Baseline Tue ⁱ or Fri ⁱ	Wk1 ^a , 2, 3 & 4 Mon ^a , & Wed	Wk1, 2,3 & 4 Fri	Wk 5 Mon Final Laser Rx	Wk 5 Tue Final Laser on Board Assess ments	Wk 8	Wk 12	Wk 16	6 month Safety Follow Up post last laser	Early Exit
Visit Window						+/- 1wk	+/- 1 wk	+/-1 wk	+/- 2 wk	
Informed consent	X									
Treatment allocation	X									
Con Meds	X		X		X	X	X	X	X	X
Adverse Events & Concomitant Procedures		X	X		X	X	X	X	X	X
Blood pressure	X				X	X		X	X	X
LogMAR BCVA	X				X			X	X	X
LogMar VA	X		X ^c		X	X	X	X	X	X
Microperimetry	X ^h	X ^{g,c,h}			X	X		X	X	
IOP	X				X			X	X	X
Dilated fundal examination	X		X ^c		X	X	X	X	X	X
Cataract grading	X		X ^c		X	X	X	X	X	X
OCT	X		X ^c	X ^b	X	X	X	X	X	X
Fundus Colour Photography	X				X			X	X	X
Autofluorescence	X ^f				X ^f			X ^f	X ^f	X ^f
Fluorescein angiography	X ^e				X			X		X
Urine Pregnancy Test	X ^d									
NIR Laser Treatment		X	X	X ^b						

- a No NIR visit or treatment on Monday of week 1. Wednesday of Week 1 (i.e. 1st NIR treatment visit) must occur the week following the screening visit.
- b Must be done the day prior to the Final assessments visit laser on board visit
- c Must be done prior to laser treatment
- d Required for women of childbearing potential.
- e A suitable angiogram performed within 1 month prior to the baseline visit may be used
- f Must be performed prior to fluorescein angiography
- g Wednesday of Week 1 only
- h At the investigators discretion any participant that did not have microperimetry performed on the study at baseline and week 1, however had standard of care microperimetry at similar timepoints before receiving their first NIR treatment, may be approached for their consent to use this data for study analysis. Participant consent will be obtained by signing an addendum study consent form allowing for the use of this standard of care microperimetry data in the study analysis.
- i If clinics/staff are not available for baseline assessment on Tuesday or Friday, another day in the week immediately prior to starting NIR treatment may be selected, however the remaining treatment and visit schedule must be adhered to according to the protocol.

16 Appendices:

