Patients with diabetic macular oedema in one eye as defined by the eligibility criteria will receive thrice weekly 90 second treatments with NIR laser, supplied by Ellex, for 4 weeks. Twenty one patients will be sequentially allocated into three groups to receive laser doses 25, 100 or 200 mW/cm². The central 1 mm will be shielded so that the fovea will be protected in the event of any unanticipated toxic effect on the retina.

1.3.1 Primary outcome:

- Reduction in central macular thickness measured by optical coherence tomography at the conclusion of treatment and at 8 weeks compared with baseline.

1.3.2 Secondary outcomes:

- LogMAR Best Corrected Visual Acuity (BCVA)
- Time to oedema reduction
- Time to oedema recurrence
- FFA assessment of leak and capillary closure before (at baseline) and after intervention (week 5 and 16)
- Change in retinal sensitivity (dB) as measured by microperimetry from Baseline to Week 1, Week 5, Week 16 and 6 month follow up visit.

1.4 Power calculation:

This study is an exploratory study designed to provide estimates of outcomes for future studies, therefore power calculations have not been applied. Seven patients per group will be sufficient to produce these estimates and will give an indication of the effective dose range

1.5 Significance:

This study will shed light on whether a novel treatment that may complement existing treatments is safe and whether it warrants further investigation in a larger study

2 Research Plan

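### Footnote h lets an unmasked investigator choose which participants without study pre-treatment microperimetry enter the retinal sensitivity analysis, with no rule that all be approached

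*Protocol*

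**What the plan says.** Change in retinal sensitivity by microperimetry is a secondary outcome in three places in the Protocol. Section 1.3.2 lists "Change in retinal sensitivity (dB) as measured by microperimetry from Baseline to Week 1, Week 5, Week 16 and 6 month follow up visit". Section 2.2.2 lists "Change in retinal sensitivity (dB) as measured by microperimetry from Baseline to Week 5, 8, Week 16 and 6 month visit". Section 8.1 lists it again.

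Two study tests precede the first laser treatment: one at the baseline visit (Section 5.2, item i) and one on the Wednesday of week 1, before laser (Section 5.3, item b; Section 15, footnotes c and g).

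Footnote h in Section 15 deals with people who have neither. It opens "At the investigators discretion any participant that did not have microperimetry performed on the study at baseline and week 1" and adds the condition that they "had standard of care microperimetry at similar timepoints before receiving their first NIR treatment". Such people "may be approached for their consent to use this data for study analysis". It continues: "Participant consent will be obtained by signing an addendum study consent form".

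Two other statements bear on how the footnote works. Section 3.2 says "There will be no masking in this study". Section 3 describes each of Groups 1 and 2 as treated "for 90 seconds (now fully enrolled"), while Group 3 carries no such note.

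**The concern.** A change from baseline needs a baseline. For a participant with no study test before treatment, the only route into this analysis is the one in footnote h. Whoever decides whom to approach therefore decides who is analysed.

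The footnote leaves that decision to individual discretion. It does not require every qualifying participant to be asked, set a deadline, give a length for the pre-treatment window, or ask that the choice be made without sight of later results. In an unmasked study with two of three groups already enrolled, the person choosing may know how the participant fared. Even without intent, people who seemed to do well could be approached more readily than those who did not.

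At stake is the estimate of mean change in retinal sensitivity per dose group. Section 1.4 says the study exists to provide estimates for future studies, and with seven per group a few selectively included patients can move a group mean.

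**Working it through.** **No plan figure to reproduce.** The Protocol states no power, alpha, effect size or SD. The only related figure, three groups of seven giving 21, is consistent (3 × 7 = 21).

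**Who is affected.** The footnote joins baseline and week 1 with *and*. On its natural reading it covers only participants missing both study tests who also had a standard-of-care test before first treatment. Someone missing only the baseline test still has the pre-laser test in week 1. The Protocol does not say how many are affected or in which groups.

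**Can the choice follow the outcome?**
- Footnote h is written in the past tense and relies on an addendum consent form, which fits retrospective use. It fixes no time for the approach.
- Section 3.2 removes masking.
- Section 3 shows that Groups 1 and 2 had completed enrolment when this version was written. Section 2.1 reports that the first cohort had been reviewed for safety and showed signs of a possible delayed benefit, but does not mention microperimetry.

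Together these show that the rule allows the choice to come after follow-up results. They do not show that it did.

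**Size, as an illustration.** Assumptions (mine, not the Protocol's): 7 patients in a group, true mean change 0, changes normally distributed with SD 1. Of the 7, *m* fall under footnote h and are included only if their change is favourable (above 0). The other 7 − *m* are always included.

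Each affected patient is included with probability 1/2. Given inclusion, the mean change is the half-normal mean √(2/π) = 0.798 SD. If *k* of the *m* are included, the expected group mean is k × 0.798 / (7 − m + k). Hence

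bias = Σₖ C(m,k) × 0.5^m × k × 0.798 / (7 − m + k).

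- *m* = 1: 0.5 × 0.798 / 7 = 0.057.
- *m* = 3: (3/8)(0.798/5) + (3/8)(1.596/6) + (1/8)(2.394/7) = 0.060 + 0.100 + 0.043 = 0.20 (0.202 unrounded).
- *m* = 5: (5/32)(0.798/3) + (10/32)(1.596/4) + (10/32)(2.394/5) + (5/32)(3.192/6) + (1/32)(3.990/7) = 0.042 + 0.125 + 0.150 + 0.083 + 0.018 = 0.42 (0.417 unrounded).

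For scale, the standard error of a mean of seven is 1/√7 = 0.378 SD. The last column comes from 40,000 simulated one-sample t-tests per row, with a nominal 2.5% in the favourable direction. The Protocol names no test for this outcome, so that column too is only illustrative.

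| Affected patients (*m*) | Expected number analysed (7 − m/2) | Spurious mean improvement | Relative to SE 0.378 | False-positive rate |
|---|---|---|---|---|
| 1 | 6.5 | 0.06 SD | 0.15 | 3.3% |
| 3 | 5.5 | 0.20 SD | 0.53 | 7.0% |
| 5 | 4.5 | 0.42 SD | 1.10 | 15.1% |

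Selection here is complete: every affected patient with an unfavourable change is left out. Weaker selection gives smaller shifts.

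**With a fixed rule.** If all qualifying participants are approached and all consent, nobody is selected on outcome and the bias in this model is 0 SD.

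**The case against.** The best defence is that the footnote rescues data. Without it these participants would have no baseline at all. The borrowed values precede treatment, so treatment cannot have altered them, and the participant must consent. All of that stands. The risk lies in who is included, not in the baseline values.

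It is also fair to say that the outcome is secondary, the study exploratory and unpowered, and the primary OCT outcome untouched. That sets the priority low. It does not remove the point, because the wording costs almost nothing to change.

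One could reply that an analysis plan, not shown here, may deal with this. For the reporting of counts and a sensitivity analysis, that may be so. For the choice itself it cannot: data from someone who was never approached are unavailable to any analysis.

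A reader might infer more than the documents support, in three ways:

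- **That patients were selected on known outcome.** The footnote permits this, but nothing shows it occurred. Completed enrolment is not the same as known microperimetry results.
- **That the shift could be 0.23, 0.42 or 0.62 SD** from leaving out the worst one, two or three of seven. Those figures require the worst patients in the whole group to be exactly those under footnote h, or all seven to fall under it. The footnote cannot exclude anyone who has a study pre-treatment test.
- **That a safety outcome is compromised.** Section 7.1 includes microperimetry in a list of assessments introduced as safety-related, but the named safety outcomes (Sections 2.2.3 and 8.1) are loss of visual acuity and increase on OCT. Retinal sensitivity is not among them.

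**Conclusion.** The point holds in a limited form. Footnote h gives an unmasked investigator unrestricted choice over which participants lacking both study pre-treatment tests are asked to supply a substitute. Because the choice can follow the results, it opens a route to outcome-related inclusion in the retinal sensitivity analysis.

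The size depends on an unstated number of affected patients. Under complete selection on the sign of the change, with normal changes and no true effect, it runs from negligible (0.06 SD for one patient in seven) to about one standard error (0.42 SD for five). This is a range of what the rule allows, not an estimate of bias in this trial. Priority is low.

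**What to change.** Replace the discretionary wording in footnote h with a duty, keeping both of its conditions. For example: *All participants with no study microperimetry at baseline and week 1, who had a standard-of-care test within [fixed window] before their first NIR treatment, will be approached for consent, without reference to any post-baseline result.*

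- Keep the reference to week 1. Without it, non-study data could be brought in for people who already have a study pre-treatment test.
- Give the window a stated length in place of the phrase about similar timepoints. Footnote e already does this for a prior angiogram, at one month before the baseline visit. The length for microperimetry is for the sponsor to set.
- Report, per group, how many were eligible, approached and consenting.
- Show the result with study-collected baselines only beside the result that includes the substitutes.

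The cost is one footnote, a few more participants to approach with the addendum form already provided for, and one extra line of results. Some selection through participants' own consent may remain, and the counts would make it visible.
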